6.1 Inclusion Criteria

Adult patients with moderate-to-severe UC with an inadequate response to, or unable to tolerate, one or more of the following conventional therapies: oral 5-aminosalicylates, oral corticosteroids, immunomodulators; or are corticosteroid dependent.

Inclusion criteria for cohort 1:

- Aged 18 years or over
- Written informed consent to participate
- Moderate-to-severe UC, defined as:
 - SCCAI > 5 and,
 - i. A raised fecal calprotectin (> 59 µg/g) or,
 - ii. A raised CRP (> 5 mg/L) or,
 - iii. Endoscopic disease activity Mayo 2 or above,

Evaluated within 4 weeks of screening

- Commencing golimumab treatment
- Sufficient English language skills to understand the patient information sheet and consent form

Inclusion criteria for cohort 2:

- Aged 18 years or over
- Written informed consent to participate
- Receiving golimumab treatment for UC over 14 weeks (have completed 6 injections at time of screening)
- Sufficient English language skills to understand the patient information sheet and consent form

6.2 Exclusion Criteria (cohort 1 only)

- Contra-indication to golimumab: tuberculosis, severe infections or congestive cardiac failure
- Imminent need for colectomy (i.e. colectomy is being planned)
- Previous primary non-response to anti-TNF therapy in the opinion of the investigator
- Previous treatment with more than one anti-TNF therapy (excluding golimumab)

There are no relevant exclusion criteria for patients entering cohort 2.

6.4 Randomisation procedure/Code-break

This is not a randomised study. Patients who are commencing golimumab treatment will be enrolled into cohort 1. Patients who are already on golimumab maintenance therapy will be enrolled into cohort 2. This will be confirmed as an investigator as part of an eligibility review. Every patient will be appointed a sequential two-digit study number.

6.5 Withdrawal of Subjects

Participants in both study cohorts have the right to withdraw from the study at any time for any reason. The investigator also has the right to withdraw patients from the study drug in the event of inter-current illness, AEs, SAE's, SUSAR's, protocol violations, cure, administrative reasons or other reasons. It is understood by all concerned that an excessive rate of withdrawals can render the study un-interpretable; therefore, unnecessary withdrawal of patients should be avoided. Should a patient decide to withdraw from the study, all efforts will be made to report the reason for withdrawal as thoroughly as possible.

Should a patient withdraw from study drug *only*, efforts will be made to continue to obtain follow-up data (including relevant safety assessments), with the permission of the patient. Because this is a non-interventional trial there won't be an interim analysis or premature termination of the study.

Participants who wish to withdraw from trial medication (IMP) will be asked to confirm whether they are still willing to provide the following:

- Trial specific data (clinical and biochemical disease activity scores and quality of life evaluations)
- Data collected as per routine clinical practice

Patient status with regards continuation on the trial will be assessed at every visit and in cases of withdrawal an eCRF withdrawal form will be completed.

6.6 Expected Duration of Trial

The end of the trial will be defined as the date of the final database lock. Each individual subject will remain on the trial until they have completed standard induction therapy with golimumab. The visit at week 14 will be the 'end of study visit' and there will be no additional follow-up visits beyond week 14.

7 Trial Procedures

7.1 By Visit

Cohort 1

Screening visit

- Signed Informed consent
- Review inclusion/exclusion criteria
- Demographic details: age, gender
- IBD-relevant concomitant medication review (Injection site reaction review is not applicable at this visit)
- Baseline clinical (SCCAI and PRO2) and biochemical assessments (CRP, albumin and FC)
- Baseline quality of life assessment (IBD-Control)
- UC disease related details: anatomic distribution (proctitis, left-sided disease or extensive colitis) and duration of disease

Day 0 (week 0), day 14 (week 2), day 42 (week 6), day 70 (weeks 10) and day 98 (week 14)

Patients self-administer golimumab at home.

Any late golimumab administrations (within a week of the planned injection date) would not be considered to significantly impact the integrity of the trial or its results and these will not be considered protocol deviations.

Day 38-42 (week 6), day 66-70 (week 10), day 94-98 (week 14)

- Serum golimumab concentration measurement
- Anti-golimumab antibody measurement
- Injection-site reactions and IBD-relevant concomitant medication review
- Clinical (SCCAI and PRO2) and biochemical assessments (CRP, albumin and FC)
- Quality of life assessment (IBD-Control)

In cohort 1 patients commencing induction therapy with golimumab, will receive delivery of the drug and self-injection training from registered nurses under the Homecare agreement already in place. This will be identical to the standard of care provided by the NHS (both at Guy's & St Thomas' and King's College Hospitals). Routine clinical care would usually involve clinical review prior to treatment initiation and again at approximately 10-14 weeks from treatment initiation. GO-LEVEL will include clinical and biochemical assessments made at weeks 6, 10 and 14, and one of these will be arranged to coincide with their routine clinical appointment. Taking part in the study will therefore involve an additional two visits for patients, above routine clinical care. Patients will be asked to self-administer their treatment in the usual way and visits will be arranged such that trough concentrations will be measured within four days *prior* to the subsequent dose. Golimumab injections could be given on the same day as the trial visit but assessments and blood tests must be taken *prior* to self-administration.

Cohort 2

Screening visit

- Signed Informed consent
- Review inclusion/exclusion criteria
- Demographic details: age, gender
- Injection-site reaction and IBD-relevant concomitant medication review
- UC disease related details: anatomic distribution (proctitis, left-sided disease or extensive colitis) and duration of disease

Day 0 (week 0)

• Patients self-administer golimumab at home

Day 21-28 (week 4)

- Serum golimumab concentration measurement
- Anti-golimumab antibody measurement
- Clinical (SCCAI and PRO2) and biochemical assessments (CRP, albumin and FC)
- Quality of life assessment (IBD-Control)

Day 28

• Patients self-administer golimumab at home

Any late golimumab administrations (within a week of the planned injection date) would not be considered to significantly impact the integrity of the trial or its results and these will not be considered protocol deviations.

In cohort 2 patients receiving maintenance therapy with golimumab, trough levels will be measured at the next available opportunity after enrollment or at the time of loss of response. In cohort 2, a trough level measurement will be defined as a drug level taken in the final week before the patients next planned injection. Patients may be recruited to cohort 2 in the week leading up to their week 18 injection (i.e. from week 17 after initiation of golimumab onwards).

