8.2 Procedures for Assessing Efficacy Parameters

For serum trough golimumab levels, anti-drug antibodies and CRP venepuncture will be carried out with 15 ml to be drawn within three days of the subsequent golimumab dose during induction therapy (cohort 1) or one week of subsequent dose during maintenance therapy (cohort 2). Clinical and biochemical disease (calprotectin) activity assessments and quality of life measurements will be collect at weeks 6, 10 and 14 in cohort 1 and week 4 in cohort 2.

9 Assessment of Safety

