9.3 Treatment Stopping Rules

Because this is a non-interventional trial there won't be an interim analysis or premature termination of the study. The trial may be prematurely discontinued by the sponsor, chief investigator or regulatory authority on the basis of new safety information or for other reasons given by the regulatory authority or ethics committee.

10 Statistics

To determine a representative cut-off value for golimumab trough levels between the groups of patients stratified by disease activity/response a receiver-operator characteristics (ROC) curve will be created. A trade-off between sensitivity and specificity will be made to establish an adequate lower margin of the therapeutic golimumab range. This statistical plan was reviewed by an independent statistician at King's College London. Relationships between golimumab trough levels and patient characteristics and clinical parameters (albumin, serum CRP, formation of ADA's, fecal calprotectin and IBD-Control) will be evaluated.

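### The cohort 1 trough window is four days in 4.3 and 7.1 but three in 8.2, and injections up to a week late are declared harmless with no listed injection date to check it

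*Combined protocol and SAP*

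**What the plan says.** **Cohort 1 window.** The flowchart in 4.3 and the visit list in 7.1 put the samples on days 38-42, 66-70 and 94-98, with injections due on days 42, 70 and 98. Section 7.1 adds that "visits will be arranged such that trough concentrations will be measured within four days" before the following dose. If visit and injection share a day, "assessments and blood tests must be taken" before the injection. Section 8.2 gives a different window: "15 ml to be drawn within three days of the subsequent golimumab dose during induction therapy (cohort 1".

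**Late injections.** For both cohorts, 7.1 says: "Any late golimumab administrations (within a week of the planned injection date) would not be considered to significantly impact the integrity of the trial". The same assurance is given for the results, and 7.1 adds that "these will not be considered protocol deviations". No reason is given.

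**Cohort 2.** Sections 4.3 and 7.1 place the sample at "Day 21-28 (week 4" after an injection on Day 0. Section 7.1 also says that "a trough level measurement will be defined as a drug level taken in the final week before the patients next planned injection".

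**Data listed.** The actual injection date is not among the visit items (4.3, 7.1), the analysis variables (10.2) or the source data (14.1). Injections are self-administered at home, drug accountability is waived (5.4), and 5.7 plans no compliance testing beyond what the measured levels might suggest.

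**Use of the levels.** The primary objective (4.1) is a week 6 trough that predicts week 14 response. Section 10 plans a ROC curve: "To determine a representative cut-off value for golimumab trough levels between the groups of patients stratified by disease activity/response".

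**The concern.** There are two separate timing points.

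First, a sample on day 38, 66 or 94 satisfies 4.3 and 7.1 but falls outside 8.2. The exposure measurement behind the primary objective has two definitions.

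Second, the allowance for late injections (seven days) is wider than the sampling window beside it (four days). A trough threshold has meaning only for a stated time since dose. If samples taken at clearly different intervals all count as the week 6 trough, the levels entering the ROC are not like for like. The plan asserts that this does not matter, and nothing it lists would let anyone test the assertion later.

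**Working it through.** **Window.** 42 - 38 = 70 - 66 = 98 - 94 = 4 days, which reproduces the four days stated in 7.1. A three-day window would be days 39-42, 67-70 and 95-98, so the conflict with 8.2 moves one bound by one day.

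**Days since last dose at the week 6 sample.** On schedule, the injections are on days 0, 14 and 42.

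| Case | Week 2 dose | Week 6 dose | Sample | Days since last dose |
|---|---|---|---|---|
| On schedule | day 14 | day 42 | 38-42 | 24-28 |
| Week 2 dose a week late, week 6 dose on its planned day | day 21 | day 42 | 38-42 | 17-21 |
| Week 6 dose a week late, visit moved with it | day 14 | day 49 | 45-49 | 31-35 |
| Whole schedule shifted after a late week 2 dose | day 21 | day 49 | 45-49 | 24-28 |

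In the second row both anchors are met: the sample is on the calendar days and within four days before the actual next dose. The gap there is that nothing controls the interval since the previous dose. In the third row the gap is planned versus actual next dose. If the visit stayed on days 38-42, the interval would be 24-28 days, but the sample would fall 7-11 days before the actual dose.

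**Effect on one patient's level.** Assumptions: half-life h of 10, 12 or 14 days, and simple one-compartment decay with immediate absorption. The induction doses of 200 mg and 100 mg come from 5.2. Relative level at day t with the second dose on day d:

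C(t, d) = 200 × 2^(-t/h) + 100 × 2^(-(t-d)/h)

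Reference C(42, 14): 25.24, 37.52 and 50.00 for h = 10, 12 and 14.

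- Week 2 dose late, sample on day 42: C(42, 21) = 34.21, 47.41, 60.36; ratios 1.355, 1.264, 1.207, or **+21 to +36%**.
- Week 6 dose late, sample on day 49: C(49, 14) = 15.54, 25.04, 35.36; ratios 0.616, 0.667, 0.707, or **-29 to -38%**.
- Whole schedule shifted, sample on day 49: C(49, 21) = 21.06, 31.64, 42.68; ratios 0.834, 0.843, 0.854, or **-15 to -17%**. The last-dose interval is still 28 days, but the first dose is older.
- On-time sampling on day 38 instead of day 42, which the plan permits: 2^(4/h) = 1.320, 1.260, 1.219, or +22 to +32%.
- One day (three versus four): 2^(1/h) = 1.072, 1.059, 1.051, or **5-7%**.

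**Illustrative effect on the cut-off.** Section 3 cites a 21-patient observational study with week 6 medians of 5.1 and 2.1 µg/ml and an AUC of 0.79. Take lognormal levels with equal spread. The log gap is ln(5.1/2.1) = 0.887, and the SD is 0.887/(1.414 × 0.806) = 0.778. Delays are uniform over 1-7 days and unrelated to response. The late share is assumed, because the documents give none. The on-time Youden cut-off is 3.27.

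- 25% late: 3.36-3.41 if all read high (+3 to +4%); 3.06-3.11 if all read low (-5 to -6%).
- 50% late: 3.44-3.56 (+5 to +9%); 2.86-2.97 (-9 to -13%).
- AUC stays at 0.784-0.789 against 0.790.

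The model is a scale only. It does not reproduce the cited study's own cut-off of 2.6.

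**Cohort 2.** If Day 0 is the actual last injection, sampling on days 21-28 is correctly timed whatever came before. The text does not say so, and it defines the trough by the next planned injection.

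**The case against.** The best defence is that 7.1 is already dose-relative: visits are arranged before the subsequent dose and blood is taken before injecting, so the day numbers are just the on-time schedule. A patient dosed late really has the measured pre-dose level, and relating actual exposure to outcome is the purpose of the study. The shift in the cut-off is small beside sampling error. Under the same lognormal model with 42 patients (assumed 21 per group, 5,000 runs), the estimated Youden cut-off has a 95% range of about 1.7 to 6.0. On-time sampling across the permitted window already varies by 22-32%. The eCRF is not shown and may hold the dates. The one-day conflict is editorial.

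Most of this stands, and it limits the size of the point. It does not close it. The sentence in 7.1 leaves planned versus actual open and is silent on the previous dose. A true pre-dose level at 17 days is not comparable with one at 35 days when the product is a single threshold. A possible unlisted eCRF field is not a plan to record or use the date.

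A reader might infer that a late dose always sets the calendar days against the dose-relative rule. It does not: with a late week 2 dose and a punctual week 6 dose, both are met.

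**Conclusion.** Both points hold, at modest size. The three- versus four-day conflict is certain from the text and is worth 5-7% of the level. The late-dose rule lets samples from 17 to 35 days after the last injection count alike as week 6 troughs. Individual end-of-window differences run from +21 to +36% down to -29 to -38%, and are -15 to -17% when the whole schedule shifts. These percentages rest on an assumed 10-14 day half-life and a one-compartment model.

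A reader might infer that the ROC cut-off is materially biased, or biased in a known direction. The documents do not support that. The share of late doses is not given, the cases act in opposite directions, and the illustration shifts the cut-off by only 3-13% even when every late case errs the same way. That illustration also assumes that delay is unrelated to response.

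Nor do the documents show that injection dates are never collected. They show that the plan neither lists nor uses them, so the assurance in 7.1 is untested as written. In cohort 2 the point reduces to a missing definition of Day 0.

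**What to change.** 1. Reconcile 4.3, 7.1 and 8.2 to one cohort 1 window.
2. State in 7.1 whether the visit follows the planned or the actual next dose.
3. Record at each existing sampling visit the sample date and the actual injection dates: both induction injections at week 6, and the last injection at later cohort 1 visits and in cohort 2. State that cohort 2 Day 0 is the actual last injection.
4. Replace the assurance in 7.1 with a statement that late injections are recorded and examined.
5. Keep all samples in the main ROC. Add time since dose to the predictor analyses in 10.2.
6. Pre-specify one supportive sensitivity ROC. For week 6, restrict it to patients whose two induction injections and sample all fall on the planned schedule. A filter of 24-28 days since the last dose is not enough, because it keeps the shifted-schedule sample that reads 15-17% low. For later cohort 1 visits, restrict to 24-28 days since the actual last dose (25-28 if the three-day window is kept); for cohort 2, to 21-28 days.

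The cost is a few date fields at visits that already take place, plus wording. The sensitivity set will be smaller than the main set and imprecise, so it can only be supportive. No visit is added and no change to dosing is proposed.

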In a recent publication, Adedokun and colleagues reported a rigorous and meticulously performed a study of the pharmacokinetics and pharmacodynamics of golimumab using samples taken as part of the PURSUIT trials. As part of these analyses the authors found serum golimumab concentrations to be dose proportional and that a positive correlation exists between concentrations and efficacy outcomes (clinical response, clinical remission and mucosal healing) during induction and maintenance therapy. They then went further by using receiver-operating-characteristics (ROC) curve analysis to define serum golimumab concentrations that may serve as potential targets for treatment optimization; proposing thresholds of 2.5 µg/ml at week 6 and 1.4 µg/ml during steadystate maintenance therapy³. Prior to this, similar findings were also reported by a group from Leuven as part of an observational study of 21 patients being treated with golimumab in a clinical setting. Median golimumab concentrations were significantly higher in partial clinical responders than in non-responders at week 2 (10.0 vs 7.4 μ g/ml, p = 0.035) and week 6 (5.1 vs 2.1 µg/ml, p = 0.037). Their ROC curve analysis revealed a cut-off of 2.6 µg/ml at week 6 (90% specificity, 56% sensitivity, Area Under the Curve 0.79 [95% CI], p = 0.034) for the association with a partial clinical response after 14 weeks of treatment⁴. The authors of both of these studies highlighted the need for further prospective trials to validate their findings and add further validation to commercially available assays for the measurement of golimumab serum concentrations. Data such as these could be used to optimise the use of golimumab in clinical practice and inform prospective therapeutic drug monitoring trials employing trough levels to drive dosing.

Anti-drug antibodies were also detected in a small minority of patients (2.9%) in the PURSUIT trials and the majority of these (67.7%) were found to be neutralizing. Their occurrence was significantly less common in patients who were receiving concomitant

immunomodulators (1.1%) compared with patients who were not (3.8%). However, due to the low observed incidence it is difficult to draw conclusions regarding their impact on efficacy. Nonetheless, a clearer understanding of their impact on drug exposure and subsequently, disease activity would be of benefit in defining the optimal use and monitoring of golimumab.

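### Cohort 2 accepts any day 21–28 level as a trough with no timing adjustment, so the maintenance remission threshold is liable to sit above a true pre-dose trough

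*Combined protocol and SAP*

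**What the plan says.** Section 4.1 makes a maintenance trough threshold associated with remission a secondary objective. Cohort 2 (70 of the 112 patients, section 4.2) serves it, with one sample per patient.

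- **Cohort 2 window.** Section 7.1 says that "a trough level measurement will be defined as a drug level taken in the final week before the patients next planned injection". The flowchart in 4.3 and the visit list in 7.1 both give days 21–28, and 8.2 repeats the one-week limit. These places agree.
- **Cohort 1 window.** Section 7.1 says that "trough concentrations will be measured within four days" before the next dose, and the flowchart matches (days 38–42, 66–70 and 94–98). Section 8.2 says three days.
- **When cohort 2 is sampled.** Section 7.1 calls for the level as soon as it can be obtained after enrolment, or when response is lost. Injections up to a week late are not deviations.
- **Analysis.** Section 10 derives the cut-off from a ROC curve. The variables in 10.2 do not include days since the last dose, and no timing adjustment or sensitivity analysis is described.

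**The concern.** Seven days is a quarter of the dosing interval, and the level is still falling over those days. A sample taken before day 28 can only read above that patient's pre-dose level, so the error does not average out. It arises even when every patient injects on time and every site follows the rule.

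At stake is the meaning of the reported threshold. Section 3 wants data that can inform trials in which trough levels drive dosing, and section 10 wants a lower margin of the therapeutic range. A cut-off built from a mixture of day-21 to day-28 levels, but labelled a trough, would overstate the pre-dose level associated with remission. The protocol gives no reason for the looser window in cohort 2.

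**Working it through.** The documents state no half-life and no figure for timing error, so there is no plan figure to reproduce. The sample-size statement in 10.1 does not bear on this point.

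**Inputs.** Section 3 cites a 21-patient observational study with median levels, responders against non-responders, of 10.0 and 7.4 µg/ml at week 2 and 5.1 and 2.1 µg/ml at week 6. It also reports, from a separate pharmacokinetic analysis, that levels are dose proportional. Section 5.2 gives 200 mg at week 0 and 100 mg at week 2.

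**Assumptions.** The cited study used the same 200/100 mg doses; its week 2 sample was pre-dose; decline is log-linear; group medians can stand for a patient's curve; and induction kinetics carry over to maintenance.

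**Step 1: rate of decline.** Let x be the fraction remaining after 14 days. The 100 mg dose contributes half of what 200 mg does, so

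C6 = C2·x² + (C2/2)·x, and k = −ln(x)/14.

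- Responders: 10.0x² + 5.0x = 5.1 gives x = 0.507, k = 0.0486 per day, half-life 14.3 days.
- Non-responders: 7.4x² + 3.7x = 2.1 gives x = 0.338, k = 0.0774 per day, half-life 9.0 days.

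Ignoring the week 2 dose, k = ln(C2/C6)/28:

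- Responders: ln(10.0/5.1)/28 = 0.0240 per day.
- Non-responders: ln(7.4/2.1)/28 = 0.0450 per day.

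If that dose was given and the week 2 sample was pre-dose, these rates understate the fall, so they act as a floor.

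**Step 2: excess over day 28.** For a sample d days early the excess is exp(k·d) − 1. Averaged over a window of w days with even sampling, it is (exp(k·w) − 1)/(k·w) − 1.

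| Decline rate | Day 21 excess | Mean, 7-day window | Mean, 4-day window |
|---|---|---|---|
| Responders, k = 0.0486 | 40% | 19% | 10% |
| Non-responders, k = 0.0774 | 72% | 33% | 17% |
| Responders, week 2 dose ignored, k = 0.0240 | 18% | 9% | 5% |
| Non-responders, week 2 dose ignored, k = 0.0450 | 37% | 18% | 10% |

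Example for k = 0.0774: exp(0.542) = 1.72; the 7-day mean is 0.719/0.542 − 1 = 33%; the 4-day mean is 0.363/0.310 − 1 = 17%.

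**Step 3: effect on a ROC cut-off.** This was simulated with log-normal true troughs (log SD 0.4 to 0.8), a true optimal cut-off of 1.4 µg/ml, a true AUC of 0.75 and even sampling over seven days. All of these settings are assumed; 1.4 is borrowed from section 3 only as a scale.

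| Clearance | Cut-off (µg/ml) | AUC |
|---|---|---|
| Same in both groups, k = 0.0486 | 1.66–1.67 | 0.74–0.75 |
| Same in both groups, k = 0.0774 | 1.82–1.85 | 0.73–0.75 |
| Non-remitters faster (0.0774 against 0.0486) | 1.69–1.73 | 0.68–0.72 |
| Non-remitters faster, week 2 dose ignored | 1.55–1.58 | 0.70–0.73 |

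The cut-off rises in every case. Random timing alone costs little AUC.

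**The case against.** The window is explicit and consistent across 4.3, 7.1 and 8.2, and it suits a cross-sectional cohort recruited opportunistically. A threshold derived and later applied with final-week samples is usable on its own scale. Samples may also cluster near day 28, where the excess is zero. And a four-day window is not free of the problem: on the main figures it still carries a mean excess of 10–17%, so it removes only about half the inflation (19 − 10 = 9 and 33 − 17 = 16 percentage points).

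Much of this stands. It makes the window a pragmatic choice rather than a contradiction, and it limits what tightening can achieve. It does not remove the point: nothing in the protocol steers samples towards day 28, the stated target is a trough, and the analysis takes no account of sampling day.

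A reader might infer more than the documents support:

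- *That the protocol's own figures put the error at 40–70%.* Section 3 gives four medians and no such figure. The range is the day-21 extreme of one model.
- *That the threshold will certainly be too high.* That depends on when samples are actually drawn, and holds relative to a pre-dose trough.
- *That a fixed share of patients would be misclassified around 1.4 µg/ml.* Section 10 derives a cut-off from the trial's own data; it does not classify patients against 1.4.
- *That the result cannot be compared with the published 1.4 µg/ml.* Section 3 gives no sampling window for that figure, so this cannot be shown. Cohort 1 thresholds concern another treatment phase and another outcome, and need not match either.

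**Conclusion.** The point holds as a likely upward bias in one secondary result. Following the plan exactly allows samples up to seven days early, with no correction. If sampling is even over the window, the average excess over a true pre-dose trough is about 19–33%, or 9–18% if the week 2 dose is ignored. It would be smaller if visits fall late in the window.

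These sizes rest on medians from 21 patients and on induction kinetics. The faster rate comes from induction non-responders, who may be under-represented among patients with six injections completed. A material loss of discrimination therefore remains conditional on non-remitters clearing the drug faster, which the documents do not establish for maintenance. The primary objective is not affected.

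**What to change.** 1. Reconcile the three-day statement in 8.2 with the four-day statement in 4.3 and 7.1 for cohort 1. Then use one trough sampling window for both cohorts in 4.3, 7.1 and 8.2 where scheduling allows.
2. Keep any cohort 2 samples from days 21–23. Excluding them outright would trade recruitment for precision.
3. Record the actual dates of the last dose and of the sample. Planned dates are not enough, because late injections are tolerated.
4. Add days since last dose to the variables in 10.2 and include it in the cohort 2 threshold analysis, for example as a covariate alongside log concentration in a model for remission, with the threshold read at day 28. With one sample per patient the timing effect is estimated between patients and may be imprecise, so step 5 is needed as well.
5. Report the remission threshold with and without the day 21–23 samples.

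The cost is slightly tighter scheduling of one visit and a little more analysis. No extra visits, samples or patients are needed.
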